#### 6.3.7 Life-style and other restrictions

#### **Contraception**

The safety of saypha®VOLUME Lidocaine for use during pregnancy has not been established, so females of childbearing potential should use contraception or avoid unprotected sexual intercourse

CFOMA est. 1976

throughout the clinical investigation. Any pregnancy occurring during the subject's participation in the investigation will be reported as an AE and followed-up as described in Section 14.6.

#### Other restrictions

The following restrictions apply to all subjects:

- Make-up should not be applied for 12 hours after injection;
- Prolonged exposure to sunlight or UV radiation must be avoided for 36 hours after injection; day care with UV protection should be used daily throughout the entire clinical investigation;
- To minimise the risk of product mobility, the subject should be advised to avoid massaging the treatment site or applying pressure to this area for one week following the injection;
- Subjects should abstain from frequent solarium visits;
- Subjects should abstain from alcohol on injection days.
- Use of saunas or Turkish baths is prohibited for one week after the injection.

#### 6.3.8 Medical care upon termination of the clinical investigation

The study participants will not receive any study-specific treatment after the final visit. Any further treatment, if needed, will be proposed to the subject by the investigator at their discretion.

#### 6.3.9 Screening/baseline failures

Data for screening/baseline failures (screened subjects who did not receive investigational device for whatever reason) will be collected in source documentation at the site and documented in the Screening log but will not be entered into the eCRF.

#### 6.3.10 Subject identification, privacy and data confidentiality

Subjects' privacy and data confidentiality will be protected in line with the principles of good clinical practice, the European Data Protection Directive and other applicable international and national requirements. Subjects will provide authorisation for use of their personal data in accordance with the applicable regulations regarding privacy and data protection. A unique numerical subject identification code will be assigned to each subject at screening. The investigator will assign the codes in ascending order, in line with the order of the informed consent date and time. The investigator must ensure that anonymity of the subjects will be maintained and that their identities are protected from unauthorized parties. In the eCRF or any other document submitted to the Sponsor or Sponsor's representative, subjects must be identified only by their identification codes; use of names, initials, complete birthdates, addresses, telephone numbers, electronic addresses or similar information is prohibited. The investigator will keep the Subject Identification Log (including complete name, date of birth, and contact details of each subject) in their file. The investigator must maintain these documents in strict confidence. All subjects will be informed and consented regarding the access to their personal investigation related data by the monitors, auditors and inspectors of the clinical investigation, as well as transmission of their coded data to the Sponsor or Sponsor's representative and data retention for the duration defined in Section 8.3. Professionals with access to subjects' data for monitoring, audits and inspections are bound to preserve strict confidentiality. This CIP, other investigation-related documentation, collected data and all other information generated will be held in strict confidence. No information concerning the clinical investigation, or the data will be released to any unauthorized third party without prior written approval of the Sponsor.

#### 6.4 Assessments and procedures

Assessments and procedures that will be performed during the investigation are described below. The exact timing of each assessment is indicated in Table 1. Schedule of procedures and events and in section 6.1.6.

It is the investigator's obligation to assure documentation of all relevant data in the subject's medical record, such as informed consent, subjects eligibility, medical history and concomitant diseases, date of enrolment into the clinical investigation, visit dates, results of examinations, application of medical device, and AEs.

#### 6.4.1 Demographic data

The following demographic data will be collected: date of birth, gender and race.

#### 6.4.2 Medical history

Medical history will be collected at Day 0, from subject interview and medical records (if available), covering relevant past medical history with particular reference to facial aesthetic or surgical procedures.

#### 6.4.3 Pregnancy test

In females of childbearing potential, including women who are postmenopausal for less than 12 months, a urine pregnancy test will be performed using a dipstick test with sensitivity of  $\leq$ 20 mLU of human chorionic gonadotropin per mL. The result will be recorded in the subject's medical record and the eCRF. This test must be done at each on-site visit except visits 2 and 4 which will be performed by telephone communication approximately 24h post-treatment.

#### 6.4.4 Photography

Clinical photography of the subject's face will be taken by the investigator or their designee using the 3D LifeViz mini camera with dual beamer pointers (Quantificare).

A standardized procedure for study photography, which will be described in a separate Photo Manual, will be provided to the investigators. This Photo Manual will ensure consistency of the background, camera settings, lighting, and subject position between the visits and across the sites. Obtained photographs must be immediately uploaded to a secure storage system and a backup copy keep in the investigator physician's computer.

#### 6.4.5 NLF-SRS grading of nasolabial folds

NLF-SRS is a validated, 5-point rating scale ranging from Grade 0 (none) to Grade 4 (extreme) as outlined in Table 3. The visual guide is provided in Figure 1. The severity of nasolabial folds will be evaluated by the investigator according to the NLF-SRS. The left and right nasolabial fold will be separately graded, and the assigned grades will be recorded in the subject's record and the eCRF.

CROMA NLF- SRS grade	Description
0	None/minimal: No visible/minimal nasolabial folds
1	Mild: Shallow but visible nasolabial fold with a slight indentation
2	Moderate: Moderately deep nasolabial fold
3	Severe: Very deep nasolabial fold with prominent facial feature
4	Extreme: Extremely deep and long nasolabial fold with skin redundancy

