#### 3.3 Justification for the clinical investigation

The current clinical investigation is designed to evaluate the performance of saypha® VOLUME Lidocaine for the correction of nasolabial folds using injection into the deep dermis or supraperiostal and to compare two different manufacturing sites.

In addition, this investigation should support the approval by obtaining clinical data on the performance and safety of saypha® VOLUME Lidocaine for the correction of nasolabial folds.

A prospective, non-comparative design was selected because it allows for the most efficient collection of clinical data on the investigational device, in a manner which is appropriate to address the purpose and objectives of the present investigation. In the absence of spontaneous improvement of nasolabial folds, it is reasonable to assume that the treatment effect can be adequately assessed by comparing the post-treatment observations versus baseline, eliminating the need for a control group. The randomization regarding manufacturing site, C1 and HQ, will be performed according the ratio 1:1 to present the results of the two manufacturing sites descriptively.

The primary performance endpoints are based on evaluation using a validated 5-point scale for assessment of severity of nasolabial folds, the Nasolabial Folds Severity Rating Scale (NLF-SRS), and is set at 24 weeks after administration of the device to address the minimum required durability of effect. Follow-up is extended a maximum up to 104 weeks, to get additional information on long-term effects and to evaluate the aesthetic outcome. Information on occurrence of pain will be primarily obtained by collection of AEs, with additional insight into pain intensity being obtained directly after the injection using a validated 11-point Numeric Pain Rating Scale (NRPS).

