#### 6.1.2 Primary performance endpoints

The performance of the investigational device will be evaluated using the following primary endpoints (see section 7.4.1) (justification is provided in Section 3.3):

• The proportion of subjects with the NLF-SRS grade reduced by ≥1 point versus baseline at Week 24, within each manufacturing site, C1 and HQ, separately and for the whole analysis population.

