# 6.1.6.5 Week 4 (Visit 5), Week 24 (Visit 6), Week 36 (Visit 7), Week 52 (Visit 8), Week 65 (Visit 9, optional), Week 78 (Visit 10, optional) and Week 104 (Visit 11, optional) Visits

The following assessments will be performed respectively 4 weeks ( $\pm$  4 days), 24 weeks ( $\pm$  7 days), 36 weeks ( $\pm$  7 days) and 52 weeks ( $\pm$  7 days) and 65 weeks ( $\pm$  7 days), 78 weeks ( $\pm$  7 days) and 104 weeks ( $\pm$  7 days) after Visit 1 (last 3 visits are optional):

- Photography
- Urine pregnancy test (in women of child-bearing potential)
- NLF-SRS grading of nasolabial folds by the investigator
- GAIS assessment by the investigator
- GAIS assessment by the subject
- Subject satisfaction
- Assessment of aesthetic effect by the investigator
- Adverse events
- Concomitant medication

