#### 6.4.7 Assessment of aesthetic effect

The investigator will assess whether the aesthetic effect is still present in the subject. A liveassessment of the treated areas will be performed and the treated areas will be compared to the subject's photographs obtained at the Baseline Visit. The presence of the aesthetic effect will be recorded as either "Yes" or "No" in the subject's medical record and in the eCRF. If a subject no longer has an aesthetic effect as of Week 52, this may prematurely lead to the termination of the clinical examination of the respective subject.

In this case new injections can be placed at previously injected locations.

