3.4.3.2 Statistical analyses

The performance analyses will be done in the Intent-to-treat population. Additionally certain analyses will be presented for the per-protocol population also to provide sensitivity analyses in the final analysis.

Individual NLF-SRS grades per visit will be calculated as the mean of grades assigned to the left and the right NLF, respectively, for descriptive summaries.

The improvement over Baseline in the NLF-SRS grade assessed by the investigator will be computed for each subject by subtracting the NLF-SRS grade obtained at each post-baseline time point from ipsilateral NLF-SRS grade obtained at Baseline. The individual improvement per visit will be calculated as the mean of both improvements in the left and the right NLF, respectively, for descriptive summaries.

The response rate will be calculated as the proportion of subjects with NLF-SRS improvement (i.e, reduction in NLF severity grade) of a \geq 1 point in both NLFs. The proportion of subjects with NLF-SRS improvement of \geq 2 points in both NLFs will be determined accordingly.

Two-sided 95% confidence intervals for the percentages of responders at various time points will be given for the proportions of the NLF-SRS improvements of ≥ 1 or ≥ 2 points, respectively using the large sample normal approximation. Also, two-sided 95% confidence intervals for the mean of individual NLF-SRS improvement at various time points will be calculated assuming normal distribution.

Summaries will be provided for the whole analysis population, as well as within each manufacturing site, C1 and HQ, separately.

Primary performance outcome measures

For the primary performance outcome measure, the percentage of responders with a \geq 1-point improvement over Baseline on the NLF-SRS based on investigator's live assessment at Week 24, the following will be given by manufacturing site and for the whole analysis population:

• percentage of responders with a ≥1-point improvement over Baseline on the 5-point NLF SRS, based on investigator's live assessment at Week 24 after initial treatment,

Secondary performance outcome measures

For secondary performance outcome measures the following will be given by manufacturing site and for the whole analysis population:

 percentage of responders with a ≥1-point improvement over Baseline on the 5-point NLF SRS, based on investigator's live assessment at Week 4, 36, 52 and optional at Week 65, 78 and 104 after initial treatment,

Page 17 of 21

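### The live Week 24 NLF-SRS grade that decides the primary endpoint is not required to be recorded before the investigator consults the Day 0 grades or baseline photographs, so the response rate may be biased, most plausibly upward

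*Protocol*

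**What the plan says.** **Endpoint and rater.** Protocol 6.1.2 defines the primary endpoint as "The proportion of subjects with the NLF-SRS grade reduced by ≥1 point versus baseline at Week 24". SAP 3.4.3.2 requires the improvement in both folds and takes it "based on investigator's live assessment at Week 24 after initial treatment". Protocol 6.4.5 names the rater: "The severity of nasolabial folds will be evaluated by the investigator according to the NLF-SRS". Each fold is graded separately, and "the assigned grades will be recorded in the subject's record and the eCRF".

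**What else happens at that visit.** The list in Protocol 6.1.6.5 covers Week 24. Its third item is "NLF-SRS grading of nasolabial folds by the investigator", its fourth is the investigator's GAIS, and its seventh is "Assessment of aesthetic effect by the investigator". Protocol 6.4.7 says how the last of these is done: "the treated areas will be compared to the subject's photographs obtained at the Baseline Visit". Under Protocol 6.4.4 a backup of the photographs stays on the investigator's computer.

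**Design.** Protocol 3.3 argues that "it is reasonable to assume that the treatment effect can be adequately assessed by comparing the post-treatment observations versus baseline" and on that ground dispenses with a control group. The SAP introduction describes the investigation as open.

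**Independent reading.** Protocol 6.4.10 provides for a photographic reviewer who is separate from the sites and uses the same scale, with a blinded evaluation at the end of the study. The resulting responder rate is an exploratory endpoint.

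**The concern.** The NLF-SRS is meant as an absolute grade: the rater looks at the fold, consults the visual guide and assigns 0 to 4. The responder status is then derived by subtraction. That separation holds only if the follow-up grade is given without reference to the first one. Here the same person may have the Day 0 grade and photographs open, and must use the photographs at that visit for another rating. The grade can then be given as an answer to whether the fold has improved by one step, with the success threshold in view.

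Subjects enter with each fold at 2 or 3 (Protocol 6.3.4). A Week 24 grade of 2 is therefore a response if Day 0 was 3 and a non-response if Day 0 was 2, and sight of the baseline tells the rater which applies. Because both folds must improve, one borderline step on one fold can change a subject's status. With no control group, a shift in grading does not cancel, and a larger sample does not reduce it.

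**Working it through.** **1. Is there an order rule?** Neither document says that the NLF-SRS comes first or that the Day 0 grades and photographs stay closed until it is entered. The order of the list in Protocol 6.1.6.5 cannot stand in for a rule, because the lists are not sequences. The baseline list in 6.1.6.1 puts the evaluation of eligibility criteria before the NLF-SRS grading, although eligibility under 6.3.4 depends on that grade.

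**2. Does the existing check cover it?** The places that specify the photographic responder rate differ on the visit that matters:

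- Protocol 6.1.4 and the exploratory list in SAP 3.4.3.2 include Week 24.
- The Protocol Synopsis and SAP 1.2.3 go from Week 4 to Week 36 and leave Week 24 out.
- Protocol 6.4.10 places the blinded evaluation at the end of the study, while Protocol 8.4 and SAP section 4 plan a formal report after Week 24. That report may therefore rest on the live grade alone.
- No text names this reading as a sensitivity analysis of the primary endpoint, and 6.4.10 does not say what the reviewer is blinded to.

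**3. The plan's own interval.** Inputs from Protocol 7.1: response rate p = 0.90, n = 50 per manufacturing site, two-sided 95%, normal approximation.

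- n = 50: 1.96 × √(0.90 × 0.10 / 50) = 0.083, giving 0.817 to 0.983. This reproduces the stated interval.
- n = 100 (whole population, also part of the primary endpoint): 1.96 × √(0.90 × 0.10 / 100) = 0.059, giving 0.841 to 0.959.

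These widths describe sampling error only.

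**4. Illustration of size.** Let f be the share of true non-responders graded as responders because the baseline is in view. The documents give no value; f = 0.10 to 0.30 is an assumption. Observed rate = p + f(1 − p).

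| f | Observed if true rate is 0.90 | True rate if 0.90 is observed: (0.90 − f)/(1 − f) |
|---|---|---|
| 0.10 | 0.91 (+1 point) | 0.889 |
| 0.20 | 0.92 (+2 points) | 0.875 |
| 0.30 | 0.93 (+3 points) | 0.857 |

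At a true rate of 0.90, this is 0.5 to 1.5 subjects in 50, or 1 to 3 in 100. With 0.90 observed, the true rate falls below the lower 95% limit only if f exceeds (0.90 − 0.8168)/(1 − 0.8168) = 0.45 for n = 50, or (0.90 − 0.8412)/(1 − 0.8412) = 0.37 for n = 100.

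**5. Opposite errors.** If a share g of true responders is downgraded, the net shift is f(1 − p) − gp. It is zero at g = f × 0.10/0.90, which is 1.1% for f = 0.10 and 3.3% for f = 0.30.

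**The case against.** The case against has several parts, and much of it stands.

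- **The plan already lists the grade first.** Protocol 6.1.6.5, Protocol Table 1 and SAP 2.3 all put NLF-SRS above the GAIS and the aesthetic effect. A reader might infer that the plan calls for grading from the photographs. It does not: it leaves the order open, and that is the whole of the defect.
- **An independent reading exists.** A reader might infer that nothing checks the live grade. That would be wrong in view of Protocol 6.4.10. What remains is that the check is exploratory, late, and inconsistent on Week 24.
- **Direction is not shown.** A reader might infer that sight of the baseline can only raise the rate. It may also reveal that little has changed, and step 5 shows that a small amount of downgrading offsets the effect. Upward is the more plausible direction when the treating side rates an open study, but the documents do not prove it.
- **The anchor cannot be fully removed.** With Day 0 hidden, the rater still knows the subject was treated and that entry grades were 2 or 3, so that 0 or 1 is always a response and 3 never is. The rater may also remember the subject.
- **No formal decision depends on it.** Protocol 5.2 plans no hypothesis test, and both manufacturing sites are graded by the same procedure, so there is no evident reason for a difference between C1 and HQ.
- **Operational documents were not seen.** The eCRF instructions or site training may set the order. The gap is established for the protocol and SAP only.

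None of this supplies a binding order for the primary measurement.

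**Conclusion.** The concern holds as a risk of bias in the primary measurement, not as a demonstrated error. The Week 24 grade comes from an unmasked investigator in an open, uncontrolled before-after study. The baseline is available, and a comparison with it is required at the same visit. No rule makes the grade come first.

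The size cannot be estimated from the documents. At the plan's 90% rate, and with upgrading of 10-30% of true non-responders assumed, the rate rises by 1-3 points. That is smaller than the sampling half-widths of 8.3 and 5.9 points, but the interval does not include it.

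A reader might infer a larger figure, up to 6 points. That needs a true rate of 80% and f = 0.30 (0.30 × 0.20 = 0.06), whereas the plan assumes 90%. Nor do the documents support the view that the planned result is invalid. The point is a cheap improvement to how the study's main estimate is measured.

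**What to change.** - In Protocol 6.4.5 and 6.1.6.5, state that at each follow-up visit the investigator grades and enters both folds from the live face and the Figure 1 visual guide before opening the Day 0 grades or photographs, and makes the GAIS and aesthetic-effect ratings only afterwards.
- Set the eCRF so that the NLF-SRS entry page does not show earlier grades.
- In the SAP, name the blinded Week 24 photographic responder rate as a sensitivity analysis of the primary endpoint. Add Week 24 to the photographic endpoint in the Protocol Synopsis and SAP 1.2.3, to agree with Protocol 6.1.4 and SAP 3.4.3.2.

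The cost is one paragraph, a site instruction, a display setting and small SAP and Synopsis edits. No rater, visit or procedure is added. Sites must keep a fixed order, and the response rate may come out slightly less favourable. The change reduces the bias; it does not remove it, because the rater still knows that the subject was treated and the range of entry grades.

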#### Table 3. Nasolabial Folds Severity Rating Scale (NLF-SRS)

[figure not shown]
Figure 1: Visual guide for Nasolabial folds severity rating scale (NLF-SRS)

#### 6.4.6 Aesthetic improvement/GAIS assessment

СГОП

The aesthetic improvement after correction of nasolabial folds will be evaluated at Week 4, 24, 36 and 52 and optional at week 65, 78 and 104 by the investigator and also by the subject using the Global Aesthetic Improvement Scale (GAIS), presented in Table 4, and recorded in the eCRF.

In case a scheduled on-site visit is not possible due to COVID-19 pandemic situation, the investigator will record the scores for GAIS assessment by the subject as reported by the subject via phone. The correctness of the latter recods will be confirmed by the subject during the next possible on-site visit with his signature. The countersigned subject questionnaire has to be kept with the source data and must not to be transferred into the TMF.

#### 6.4.7 Assessment of aesthetic effect

The investigator will assess whether the aesthetic effect is still present in the subject. A liveassessment of the treated areas will be performed and the treated areas will be compared to the subject's photographs obtained at the Baseline Visit. The presence of the aesthetic effect will be recorded as either "Yes" or "No" in the subject's medical record and in the eCRF. If a subject no longer has an aesthetic effect as of Week 52, this may prematurely lead to the termination of the clinical examination of the respective subject.

In this case new injections can be placed at previously injected locations.

#### 6.4.8 Pain assessment

After initial administration and optional Touch-up treatment of the investigational device, the subject will be asked by the investigator to quantify the pain associated with the procedure by means of a semiquantitative 11-point Numeric Pain Rating Scale (NPRS), where 0 corresponds to no pain, and 10 to the worst pain imaginable. Pain intensity will be assessed twice, immediately after injection, and approximately 15 (±5) minutes thereafter, by asking the subject one of the following questions, as appropriate:

- "How would you rate the pain you have felt during the treatment, if "0" is no pain at all, and "10" is the worst pain you can imagine?"
- "How would you rate the pain you have felt during recovery from the treatment, if "0" is no pain at all, and "10" is the worst pain you can imagine?"

Subject's response will be recorded in the Pain assessment form and the eCRF. To avoid over-reporting of pain, a non-leading question *"How do you feel?"* should be asked prior to pain assessment. Only spontaneously reported pain, or pain graded  $\geq$ 4 will be recorded as an AE.

